Cushing's syndrome is an endocrine disorder caused by excessive production of glucocorticoids. In 10%-20% of patients this syndrome results from ectopic production of ACTH and very rarely from ectopic CRH production (1-6). Small cell carcinoma of the lung, islet cell tumor of the pancreas, medullary thyroid cancer, pheochromocytoma, and foregut carcinoid tumors are the most common sources of ACTH production (1,2,5,7). The mean age at diagnosis in patients with ectopic ACTH production is 40 years and the male-female ratio is almost 1:1 (1,8). The ectopic source of ACTH production cannot be found in 50% of patients despite aggressive, extensive, and expensive testing (9,10). These patients are at high risk of death due to sepsis, hypertension, gastrointestinal pathology, and metastatic dissemination (8,11). More than 50% of patients with ectopic ACTH production cannot be treated surgically or fail medical therapy and therefore, they finally undergo adrenalectomy with life-long hormone replacement therapy (8). However, if the source of ectopic ACTH production is found before the tumor metastasizes, resection is usually curative. Thus, the ability to image primary and/or metastatic lesions has proved to be the key to successful treatment. Conventional imaging is generally performed with computerized tomography (CT) and magnetic resonance imaging (MRI) of the chest and abdomen. ¹²³I-Metaiodobenzylguanidine (MIBG) is taken up by adrenal tissue and pheochromocytomas and may be useful in identifying this source of ectopic ACTH secretion. As discussed below, other modalities, including somatostatin receptor scintigraphy and various positron emission tomography (PET) ligands, also may be useful in the localization of these tumors.

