The research L OCT scan will be performed in the same manner as the clinical study, except that SPECT/CT of any one area will only be performed up to 2 times. All other SPECT studies of the area will be performed without CT. No clinical H-OCT study will be performed on these patients within one year of the research L OCT study.

Evaluation and treatment at the conclusion of imaging episodes

The investigators will review the results of all imaging studies at the end of each admission. Imaging results will be correlated; as is typical in standard medical care, we will not blind the reader of any conventional images to other results. However, the F-DOPA PET/CT, studies will be read without knowledge of the results of conventional MRI and CT studies. If the conventional imaging studies localize a possible tumor, the patient will undergo surgical resection, probably during a subsequent admission. If the conventional imaging studies are equivocal, or if only the research studies suggest a tumor, additional studies will be performed as clinically indicated. These studies may include repeat CT scan focused on the area of concern, venous sampling for ACTH measurement in chest or abdominal vessels, ultrasound examination, bone scan, MIBG scan, fine needle biopsy or other tests. The patient will not undergo surgery unless additional studies reveal a mass. Thus, at the conclusion of each episode of evaluation (and possible treatment), some patients with positive imaging will have surgical confirmation of the source of ectopic ACTH secretion. All others will be non-localized. These patients will receive treatment for hypercortisolism (usually medical, but adrenalectomy may be chosen), and will return to the Clinical Center to have repeated CT and MRI imaging (every 6-12 months) and repeated F-DOPA

Clinical Center to have repeated CT and MRI imaging (every 6-12 months) and repeated F-DOPA PET/CT and OCT (every 12 months).

If Cushing syndrome recurs or if patients are not cured by initial resection, patients are offered re-evaluation to localize any residual tumor or recurrence. In that case, all clinical, biochemical, and imaging tests may be repeated similar to the initial visit. Upon completion of the study, the patients are returned to the care of their referring physician.

Concern about radiation dose

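### No rule says which CT/MRI read is compared with F-DOPA in objective (a), and no masked read of the post-mifepristone Octreoscan is specified for objective (c)

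*Combined protocol and SAP*

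**What the plan says.** The section *Evaluation and treatment at the conclusion of imaging episodes* sets different conditions for the two sides of objective (a). For conventional images, "as is typical in standard medical care, we will not blind the reader of any conventional images to other results". For the new test, "However, the F-DOPA PET/CT, studies will be read without knowledge of the results of conventional MRI and CT studies". The Introduction uses the term for CT and MRI: "Conventional imaging is generally performed with computerized tomography (CT) and magnetic resonance imaging (MRI) of the chest and abdomen". Whether the standard 6 mCi Octreoscan (L-OCT) is included is not stated.

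The same section describes the work-up. Where "if only the research studies suggest a tumor, additional studies will be performed as clinically indicated", the protocol adds: "These studies may include repeat CT scan focused on the area of concern". Venous sampling, ultrasound, MIBG and biopsy are among the other options. Then: "The patient will not undergo surgery unless additional studies reveal a mass". Patients whose tumor is not localized return for "repeated CT and MRI imaging (every 6-12 months").

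*Data Collection and Evaluation* makes exploration and pathology the reference standard, names McNemar's test, and compares F-DOPA with the other modalities in proven tumors. Overlapping confidence intervals are to be taken as showing similarity. Nothing says whether the first, a prompted or a follow-up CT/MRI read is used.

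For objective (c), only patients with a negative first L-OCT receive mifepristone and a second L-OCT. The result is a descriptive conversion percentage, compared post hoc with the historical high-dose figure (7 of 12 low-dose negatives, Introduction). *Source Documentation and Case Report Forms* has research scans reviewed with the study radiologist. No masking of the second L-OCT read is mentioned anywhere.

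**The concern.** Tumors seen by F-DOPA and missed by CT/MRI are the evidence that F-DOPA adds something. The Introduction drops FDG PET because it found nothing that CT or MRI had not. Under the surgery condition above, a lead seen only on research imaging becomes a pathology-proven tumor only after another study has shown a mass. If that study is the prompted CT, and it is scored as a CT detection, the patient moves from F-DOPA only to both positive. A follow-up CT or MRI read with the earlier F-DOPA result in hand can do the same. F-DOPA could then appear to add little because of how reads were recorded.

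In (c), the second L-OCT may be read by someone who knows that the first was negative and that mifepristone was given. There is no concurrent control, so a reader's expectation of conversion goes straight into the percentage.

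**Working it through.** **Objective (a): direction.** The documents give no paired table and no power calculation for (a), so there is no figure to reproduce. Crediting a share *f* of F-DOPA-only detections to CT/MRI moves *f* × p10 from the F-DOPA-only cell to the both-positive cell. F-DOPA sensitivity is unchanged and CT/MRI sensitivity rises, so the difference shrinks.

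A hand check on an assumed table of 30 proven tumors (10 both, 8 F-DOPA only, 1 CT/MRI only, 11 neither):

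- No patient moved: 18/30 v 11/30, discordant 8 v 1, exact two-sided p = 2 × (1 + 9)/2^9 = 0.039.
- One patient moved: 18/30 v 12/30, discordant 7 v 1, p = 2 × (1 + 8)/2^8 = 0.070.

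**Objective (a): size under assumed inputs.** Power is the probability that exact two-sided McNemar p < 0.05 with F-DOPA ahead, by full enumeration of the four cells.

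- Scenario A (assumed): both 45%, F-DOPA only 40%, CT/MRI only 5%, so 85% v 50%. The 85% is the top of the 50-85% range that the Introduction quotes for DOPA PET in other tumors.
- Scenario B: both 40%, F-DOPA only 15%, CT/MRI only 5%, so 55% v 45%. The 55% is the rate in *Justification of the number of subjects*; the 45% and the cell split are assumed.
- Number of proven tumors: 30 if every planned F-DOPA patient is proven. It is 0.5 × 30 = 15 if half are not, following the statement that "The ectopic source of ACTH production cannot be found in 50% of patients despite aggressive, extensive, and expensive testing".

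| Scenario | 0% credited | 25% | 50% | 100% |
|---|---|---|---|---|
| A, 30 tumors: power | 82.3% | 57.0% | 23.5% | 0% |
| A, 30 tumors: overlap rule does not show F-DOPA higher | 53.7% | 83.4% | 97.7% | 100% |
| A, 15 tumors: power | 37.8% | 16.7% | 3.6% | 0% |
| B, 30 tumors: power | 9.9% | 3.5% | 0.6% | 0% |

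In scenario B the overlap rule fails to show F-DOPA higher almost 100% of the time at every share (Clopper-Pearson 95% limits). The 0% column is due to sample size and the analysis rule alone; only the change along a row is due to which read is counted. At 100% credited the F-DOPA-only cell is empty, and McNemar cannot favour F-DOPA at any sample size.

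**Objective (c).** Let *t* be the true conversion rate, *f* here the spurious-positive rate on the second read, and *m* its miss rate. Observed conversion = t(1 − m) + (1 − t)f. The values of *t* = 0, *f*, *m* and the 12 patients below are assumed; the plan gives no sample size for mifepristone.

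- No drug effect, t = 0: observed = f, so 5%, 10% or 20%. With 12 patients the chance of at least one spurious conversion is 1 − (1 − f)^12 = 46%, 72% or 93%.
- t = 7/12, m = 20%, f = 10%: 0.583 × 0.8 + 0.417 × 0.1 = 50.8%, below the true 58.3%.

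Reading error therefore inflates the percentage only when t < f/(f + m). With m = 20% and f = 10% that is t < 33%. Here *f* covers all sources of a spurious second positive. Reader expectation is one part of it, and the documents do not allow the parts to be separated.

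**The case against.** Unmasked reading of clinical images is a stated and ordinary choice, and the new test is the one that is masked. The protocol also lists the focused CT among additional studies, separately from conventional and research imaging, so a careful analyst would probably not score it as a conventional detection. A reader might infer that the plan instructs the miscount, or that first CT/MRI reads already borrow from F-DOPA. The documents support neither: the counting rule is missing, and the order of the first reads is not stated. Ultrasound or another study could also be the one that shows the mass. What stands is that nothing in the analysis section rules the miscount out, and follow-up CT and MRI are plainly conventional imaging.

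A reader might also take the fall from 82.3% to 23.5% as the expected loss. It needs F-DOPA sensitivity far above the protocol's own 8/17 (47%) or planning rate of about 55%. At 55% v 45%, sample size and the overlap rule have already settled the comparison, and read choice costs at most 9.9 points of power. That objection stands in full as to size.

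Nor does the point undermine a finding that F-DOPA is more sensitive, since the distortion runs against F-DOPA.

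For (c), it is tempting to say that masking would remove the 46%, 72% or 93% chance of a false conversion. It would not. Ordinary reading error, scan-to-scan variation and the lack of a control remain under masked reading. The historical 7/12 also came from low-dose negatives, so part of the selection is shared. The analysis is labelled descriptive, but its percentage still goes into the historical comparison.

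**Conclusion.** The concern holds in limited form. For (a), the plan leaves open which CT/MRI read is analysed, and its own work-up and follow-up schedule generate prompted and informed reads. Counting them would understate an F-DOPA sensitivity advantage and could empty the F-DOPA-only cell. Under the assumed inputs, crediting half of those detections costs 82.3 − 23.5 = 58.8 points of McNemar power in the favourable scenario and 9.9 − 0.6 = 9.3 points at the planning rate. The true share credited is unknown.

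For (c), reader expectation can raise the conversion percentage because no masked second read is specified, only first-read negatives are rescanned, and there is no concurrent control. By how much cannot be estimated. If the drug has a real effect, missed second reads can pull the other way, so the documents do not show that the reported percentage will be too high overall.

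This should be changed because the remedy is cheap and initial reads not locked at the time are hard to recover later.

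**What to change.** **Objective (a).** Record and lock the initial CT, MRI and L-OCT reads of each imaging episode before that episode's F-DOPA result is released, and state that the locked reads enter the analysis. State whether L-OCT counts as conventional. Report an F-DOPA-prompted repeat CT or re-read separately, not as an independent conventional detection. Analyse follow-up episodes separately, or have them read for research without the earlier F-DOPA result.

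**Objective (c).** Have an existing reader score the stored pre- and post-mifepristone L-OCTs in random order, masked to date, drug and other imaging. Use an image set common to both scans in timing (4 h and 24 h) and in format. Format matters because the protocol limits SPECT/CT on the research scan and allows extra delayed images on the clinical one, either of which could reveal the order. Report the masked conversion percentage beside the clinical one. State as limitations that scan-to-scan variability is unmeasured and that masking of the historical high-dose reads is not documented.

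**Cost.** A locked score form and one batch reading session on stored images; no extra scans or radiation. Clinical reads and work-up stay unchanged. The downsides are some reader time and the chance that a reader recognises cases in a rare disease.

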We found that F-DOPA PET substantiated a lesion seen on CT and/or MRI scan in 6 of 11 patients, including some with questionable results on conventional imaging. We amended the protocol in 2008 to administer carbidopa, 200 mg, one hour before the study. [name] has found that this strategy improves tumor detection of pheochromocytoma, presumably by inhibiting decarboxylation of the tracer. This amendment will now allow us to perform FDOPA PET/CT, which was not available previously.

The project was amended in 2004 regarding the routine chest MRI scans. We initially obtained images on a 0.5 T magnet using, using STIR, T1 and T2 images. Subsequently a 1.5 T magnet replaced the lower strength magnet and STIR images were not obtained. Recently a 3.0 T magnet has become available with image acquisition gated to the EKG R-R interval so that artifact from cardiac motion is reduced. Our collaborator [name] has performed T1 and T2 sequences using this approach with excellent resolution of mediastinal and chest structures. Increased strength of magnetic field compared to conventional 1.5T MRI allows for a stronger signal and therefore improved signal to noise ratio. Free breathing techniques are used to avoid breath holding, which may be difficult for those patients with volume overload. The combination of higher signal and decreased motion artifacts should significantly improve resolution allowing for better delineation of small lesions that may be responsible for ectopic ACTH production. To test this, we have added these sequences.

We wish to clarify the use of chest CT scans, as the available modalities have changed. A “surgical chest protocol CT” (which involves thin (1-2mm) cuts throughout the thorax) will be obtained at each visit.

For the initial imaging, gated “cardiac CT” will be obtained as well to look for retrocardiac lesions that can be obscured by non-gated routine CT. However, because of the amount of radiation, we will obtain this scan only at the initial visit, unless there is a subsequent clinical suspicion of a retrocardiac lesion.

OBJECTIVES

Specific questions to be addressed:

F-DOPA PET/CT

(a) Compared to other imaging techniques, is the sensitivity and specificity of F-DOPA PET/CT higher in detecting the source of ectopic ACTH production in patients with known and unknown tumor localization?

(b) Does a correlation exist between F-DOPA uptake and the type of tumor, its size and proliferative activity?

Octreoscan

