The Pet Department's new PET/CT scanner has higher resolution and sensitivity than the older GE Advance instruments and allows us to perform a low dose CT for attenuation correction and localization.

The F-DOPA dose (12 mCi) is injected intravenously over approximately 2 minutes. During the infusion, the patient is instructed to rest quietly. After a 30 min. uptake period, patients undergo a low dose attenuation CT, followed by imaging of the pelvis through the pituitary.

The F-DOPA PET scan lasts up to ~2 hours. Patients having problems controlling their urine may need to use a Foley or condom catheter for approximately 12 hours after the injection of F-DOPA.

Octreoscan procedure

Patients are studied in the Nuclear Medicine scanning facility at the Clinical Center. Patients are encouraged to hydrate themselves well before and after administration of [¹¹¹In-DTPA-D-Phe]-pentetreotide to aid in renal elimination of unbound material.

The patient is injected intravenously with approximately 6mCi (L-OCT) or 18 mCi [¹¹¹In-DTPA-D-Phe]-pentetreotide (H-OCT) in the Department of Nuclear Medicine and is imaged 4 and 24 hours later. Whole body and SPECT/CT images are obtained. For the clinical Octreoscans, additional delayed images may be obtained if necessary. Octreotide imaging takes 1-3 hours each day, depending on the clinical situation. Patients having problems controlling their urine may need to use a Foley or condom catheter for approximately 24 hours after the injection of Octreotide. Some patients will be administered a laxative after the first day of imaging to clear bowel contents, as clinically indicated.

For the mifepristone study, mifepristone will be administered at a total daily dose of 600 mg (given as one 200 mg tablet tid, per os) starting 10 days before a second research L-OCT is performed. It will be given in the morning (before breakfast), middle of the day (either immediately before lunch for subjects who have late lunch or 2 hours after lunch for subjects who have an early lunch), and evening (either immediately before dinner for subjects who have late dinner or 2 hours after dinner for subjects who have an early dinner). Blood (8 ml) will be drawn on the morning of the second scan, and will be stored for possible measurement of mifepristone. No other medical treatment for hypercortisolism will be given during this time. A research L-OCT will then be performed.

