The IRB previously approved an accrual ceiling of 202 for the high dose octreoscan component. That component is no longer a part of the protocol. Eighty-nine patients have enrolled in the protocol. F-DOPA PET was positive in 8 of 17 patients with known tumors and high dose Octreoscan was positive in 7 of 12.

Given these encouraging results, we propose performing F-DOPA in a total of at least 30 patients. The current results imply an estimated success rate of about 55% for each modality; the plausible range for the true success rate ranges from about 26 to 80% using a 95% confidence interval, a very broad range.

Studying a total of 30 patients will allow us the possibility of precluding a true success rate of under 20% (with 95% confidence) if we were to see no additional successes. If there are additional successes in the additional patients the confidence interval for what the true probability of success could be will still be fairly broad. Since limited patients have been evaluated using F-DOPA, we ask that the overall accrual ceiling remain intact and that it be altered based on annual reports of the results. Additionally, we have essentially no data on which to base a sample size calculation for the mifepristone study, and would recalculate accrual limits when such data are available.

Data Collection and Evaluation

Staff in the Departments of Radiology will evaluate the conventional studies. [name] reviews the F-DOPA PET/CT without knowledge of the results of other localization studies. [name] reviews all studies. Data are maintained by the NICHD Clinical Trials DataBase.

The study will be analyzed in collaboration with [name] (Clinical Center Statistics Center). Data are collected and analyzed with regard to the sensitivity, specificity, accuracy, and predictive value for each scan being evaluated. The exploration and pathologic analysis is used as the reference standard. McNemar's test for evaluating paired data will be used (40). In addition to McNemar's test, other approaches to evaluation of the four objectives are below:

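### The only precision statement for F-DOPA (30 patients preclude a rate under 20%) is wrong on its own numbers, and it gives no precision for F-DOPA PET/CT, the technique in objective (a)

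*Combined protocol and SAP*

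**What the plan says.** All places are in the combined protocol and SAP.

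- **Justification of the number of subjects.** The results so far are given as "F-DOPA PET was positive in 8 of 17 patients with known tumors". The plan is then: "we propose performing F-DOPA in a total of at least 30 patients". The precision claimed for 30 is "the possibility of precluding a true success rate of under 20% (with 95% confidence) if we were to see no additional successes". The section adds that the interval will stay fairly broad if there are more successes. On numbers beyond 30 it says "we ask that the overall accrual ceiling remain intact", subject to annual reports.
- **Objectives, item (a).** The question is whether, compared with other imaging, "is the sensitivity and specificity of F-DOPA PET/CT higher in detecting the source of ectopic ACTH production".
- **Introduction.** An earlier F-DOPA PET result of 6 of 11 patients is reported. After a reference to the 2008 carbidopa change, the text says: "This amendment will now allow us to perform FDOPA PET/CT, which was not available previously".
- **F-DOPA PET/CT procedures.** The "new PET/CT scanner has higher resolution and sensitivity than the older GE Advance instruments".
- **Data Collection and Evaluation.** Accuracy measures, including "predictive value for each scan being evaluated", are to be calculated. Item (a) restricts sensitivity and specificity to patients with proven tumors. It does not say whether earlier F-DOPA PET scans enter the PET/CT estimate.

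**The concern.** There are two problems with one sentence.

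First, the lower limit looks too high. Eight successes in 30 is an observed rate of 27%, and with 30 patients the 95% interval must reach well below 20%.

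Second, the sentence describes a different set of patients from those objective (a) asks about. The condition of no additional successes makes sense only if the 30 includes the patients already scanned. Those patients are reported as F-DOPA PET, and the Introduction presents PET/CT as newly available. The protocol itself describes the new scanner as more sensitive, so it gives a reason not to treat the two techniques as interchangeable without saying so.

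At stake is whether the sponsor and the IRB know how precisely the study will answer its first question. The plan has no other size rationale for F-DOPA and no number for PET/CT.

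**Working it through.** **Inputs**
- 8 successes in 17 known-tumor patients; total of at least 30; threshold 20% at 95% confidence (sidedness not stated): Justification of the number of subjects.
- 6 of 11 earlier F-DOPA patients: Introduction.

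**Method.** Exact (Clopper-Pearson) limits for x successes in n: lower limit = Beta quantile at α/2 with parameters (x, n−x+1); upper limit = Beta quantile at 1−α/2 with parameters (x+1, n−x). For a two-sided 95% interval α/2 = 0.025. For a one-sided 95% lower limit, 0.05 replaces α/2.

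**Step 1: try to reproduce the plan's figure.** No additional successes means x = 8, n = 30, a rate of 26.7%.

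| Method | Lower limit, two-sided 95% | Lower limit, one-sided 95% |
|---|---|---|
| Exact | 12.3% | 14.0% |
| Wilson | 14.2% | 15.7% |
| Wald | 10.8% | 13.4% |

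None reaches 20%. Equivalently, P(X ≥ 8 | n = 30, p = 0.20) = 0.24, so 8 of 30 is quite compatible with a true rate of 20%. Carrying forward 7 or 6 successes instead gives still lower exact limits (two-sided 9.9% and 7.7%).

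**Step 2: what 30 patients would need.**
- Exact two-sided: 11/30 has a lower limit of 19.9% and 12/30 has 22.7%. So 12 are needed, which is 12 − 8 = 4 further successes.
- Exact one-sided: 10/30 has 19.3% and 11/30 has 22.1%. So 11 are needed, which is 3 further successes.

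**Step 3: how many of the 30 would be PET/CT.**
- If all 17 were scanned before PET/CT: 30 − 17 = 13.
- If only the 11 patients in the Introduction were scanned before it, up to 17 − 11 = 6 of the 17 could be PET/CT: 13 + 6 = 19.

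There is some sign that the text was written in layers. The stated current rate of about 55%, with a range of about 26 to 80%, fits 6/11 (54.5%; Jeffreys interval 27.0-80.0%) better than 8/17 (47.1%; exact 23.0-72.2%).

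**Step 4: precision at a rate near the plan's 55%.**

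| Patients | Successes | Exact 95% interval | Width (points) |
|---|---|---|---|
| 13 | 7 | 25.1-80.8% | 56 |
| 19 | 10 | 28.9-75.6% | 47 |
| 30 | 16 | 34.3-71.7% | 37 |

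The PET/CT interval at the floor is about 1.25 (47/37) to 1.5 (56/37) times as wide as that for 30. At 13 patients it is about the same as the 26 to 80% that the plan itself calls very broad.

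**The case against.** The best defense is that the section sizes the tracer, not the scanner. It speaks of performing F-DOPA, sets 30 as a minimum, warns of broad intervals, and keeps accrual under annual review. All of that is so. It does not rescue the 20% sentence, which fails for the tracer total as well, and it leaves objective (a) with no stated precision.

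One might also read the sentence as a limit on the new patients alone. A result of 0/13 has a one-sided 95% upper limit of 20.6%. But that would exclude rates above about 20%, the opposite of what is written.

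The count of 13 is open to challenge, and these points stand:
- The protocol uses the term F-DOPA PET loosely, even within the PET/CT procedures, so the label does not prove how the 17 were scanned. Hence the range of 13 to 19.
- The 17 are patients with known tumors, while the 30 are simply patients. If occult-tumor patients count toward the 30, fewer than 13 to 19 places remain for PET/CT in known tumors.
- Research Procedures allows a second F-DOPA study after at least 12 months, so some earlier patients may add a PET/CT scan. Accrual may also pass 30.

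Two stronger readings are tempting, and the documents support neither. A reader might infer that counting the earlier 17 could reverse a study conclusion at 20%. That threshold appears only in the size rationale; the analysis of objective (a) compares modalities by overlapping intervals. A reader might also infer that the PET/CT estimate will be biased by mixing in earlier PET scans. No section plans to pool, and the scanner comparison describes the instrument and gives no difference in tumor detection. The gap is that the plan does not say which scans enter.

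**Conclusion.** The concern holds in two parts.

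The arithmetic error is firm and rests on no assumption about scanners. With no additional successes, 30 patients give a lower limit of 12% (14% one-sided), not 20%, and no standard interval changes that.

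The mismatch with objective (a) is also real, but its size is approximate. The precision for 30 is not the precision for F-DOPA PET/CT. At the floor the PET/CT number is roughly 13 to 19, with intervals of about 25-81% to 29-76% at a rate near 55%. This assumes that the statement on availability in the Introduction applies to most or all of the 17, that the 30 counts known-tumor patients, that none of the earlier PET patients is rescanned, and that accrual stops at 30.

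The point concerns what the plan states and which scans its primary estimate uses. It does not show that the study is infeasible or that a conclusion will be wrong.

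**What to change.** **Justification of the number of subjects**
- Replace the sentence on excluding rates under 20%. With no additional successes, 8/30 gives a lower 95% limit of 12% (14% one-sided); excluding rates under 20% needs 12 of 30 (11 one-sided). State which sidedness is meant.
- Label 30 as a total for the tracer across F-DOPA PET and PET/CT, and say whether occult-tumor patients count toward it.
- State the number of PET/CT patients expected and its exact interval, with the assumptions: for example 7/13, 25-81%, or 10/19, 29-76%.

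**Data Collection and Evaluation, item (a)**
- Make F-DOPA PET/CT scans in patients with proven tumors, one per patient, the primary set for objective (a).
- Report earlier F-DOPA PET results separately, with any pooled figure marked as secondary.

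**Cost.** Wording changes, plus a check of existing records to establish which of the 17 had PET and which PET/CT. No new patients or scans are needed. The downside is a wider stated interval for the primary estimate.
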